9.5. Exploratory Analyses

10. SAFETY ANALYSES

10.1. Adverse Events

An adverse event (AE) is any untoward medical occurrence in a participant or clinical investigation participant, temporally associated with the use of a medicinal product, whether or not considered related to the medicinal product.

An AE can therefore be any unfavorable and unintended sign (including an abnormal laboratory finding), symptom, or disease (new or exacerbated) temporally associated with the use of a medicinal product.

Adverse events summaries will be constructed displaying AEs in decreasing order of frequency under the combined RVT-1401 group according to the numbers of subjects reporting the AE (not the number of events).

A listing will be constructed that includes the subject identification, the dose group, TEAEs, MedDRA terms, seriousness, severity, causality related to study medication, elapsed time to onset, duration, and outcome.

10.1.1. Adverse Event Dictionary

AE verbatim text will be coded using the Medical Dictionary for Regulatory Activities (MedDRA version 21.1). System organ class (SOC), high level group term, high level term, preferred term (PT), and lower level term will be attached to the clinical database.

10.1.2. Adverse Event Severity

Adverse events are graded by the investigator as Grade 1 (mild), Grade 2 (moderate), Grade 3 (severe), Grade 4 (life threatening) or Grade 5 (death) according to toxicity criteria specified in the study protocol. The severity grade of events for which the investigator did not record severity will be categorized as “missing” for tabular summaries and data listings and will be considered the least severe for the purposes of sorting for data presentation.

10.1.3. Relationship of Adverse Events to Study Drug

Related AEs are those for which the investigator answers “Probably Related” or “Possibly Related” to the question “Is there a reasonable possibility that the study treatment caused or contributed to the adverse event?” Adverse events for which the investigator did not record relationship to study drug will be considered related to study drug. Data listings will show relationship as missing.

10.1.4. Serious Adverse Events

Serious adverse events (SAEs) are those identified in the clinical database as such. The clinical database will be reconciled with the SAE database before database lock.

10.1.5. Treatment-Emergent Adverse Events

10.1.5.1. Definition of Treatment-Emergent

Adverse events will be classified by study part according to the following:

- Pre-treatment: AEs that either started prior to the date of the first dose of study drug or had no recorded start date and the stop date is prior to the first dose of study drug.
- Treatment-emergent: AEs that either started on or after the date of the first dose of study drug and on or before the date of 6 weeks (42 days) post the last dose of study drug or had no recorded start date and the stop date is not before the first dose of study drug.
- Post-treatment: AEs that started after the date of 6 weeks (42 days) post the last dose of study drug.
- OLE treatment-emergent: AEs that either started on or after the date of the first dose of study drug in the OLE.

10.1.5.2. Incomplete Dates

The following algorithms will be applied to missing and incomplete start and stop dates:

Start Dates:

If the day portion of the start date is missing, then the start date will be estimated to be equal to the date of first dose of study drug, provided the start month and year are the same as the first dose of study drug and the stop date is either after the first dose of study drug or completely missing. Otherwise, the missing day portion will be estimated as "01."

If both the day and month portions of the start date are missing, then the start date will be estimated to be equal to the date of first dose of study drug, provided the start year is the same as the first dose of study drug and the stop date is either after the first dose of study drug or completely missing. Otherwise, the event will be assumed to start on the first day of the given year (e.g., ??-??-2013 is estimated as 01-JAN-2013).

If the start date is completely missing and the stop date is either after the first dose of study drug or completely missing, the start date will be estimated to be the first day of study drug dosing. Otherwise, the start date will be estimated to be the first day of the same year as the stop date.

Stop Dates:

If only the day of the stop date is unknown, the day will be assumed to be the last of the month (e.g., ??-JAN-2013 will be treated as 31-JAN-2013).

If both the day and month of the stop date are unknown, the stop date will be assumed to be last day of the year (e.g., ??-??-2013 will be treated as 31-DEC-2013).

If the stop date is completely missing, and the stop date will be imputed using the last known date on the study.

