10.1.6. Summaries of Adverse Events

All AE summaries will be provided separately for the double-blind treatment period and the follow-up period as well as the OLE treatment period and OLE follow-up period. Double-blind treatment period AE summaries will present treatment-emergent AEs which occurred before study drug administration during OLE study period or before the primary lock date, whichever comes first. Follow-up period AE summaries will present post-treatment AEs, OLE treatment period AE summaries will present OLE treatment-emergent AEs which occur before or on week 12 visit and OLE follow-up period AE summaries will present OLE post-treatment AEs. Pre-treatment AEs will be listed.

Overall summaries of treatment-emergent AEs by treatment group will be provided to include the number and percentage of subjects who:

1. Had any AE,
2. Had any Grade 3 or higher AE,
3. Had any treatment-related AE,
4. Had any Grade 3 or higher treatment-related AE,
5. Had any SAE,
6. Had any treatment-related SAE,
7. Permanently discontinued from study drug due to an AE, and
8. Died.

Summaries (number and percent of subjects) of treatment-emergent adverse events (by SOC, and PT) will be provided by treatment group for the following:

- All AEs,
- All Grade 3 or higher AEs,
- All treatment-related AEs,
- All Grade 3 or higher treatment-related AEs,
- All SAEs,
- All treatment-related SAEs,
- All AEs that leading to permanently discontinued from study drug.

Multiple events will be counted once only per subject in each summary. For data presentation, SOC will be ordered alphabetically, with PT sorted by decreasing frequency in

the combined RVT-1401 column. Treatment period and follow-up period AE summaries will be provided for the SAF analysis population. Open-label extension AE summaries will be provided for the OLE analysis population. Whole study AE summaries include the double blinded period, OLE period and follow up will be provided for below 3 tables:

- Overall summaries of treatment-Emergent AEs
- Treatment-emergent AEs by SOC and PT
- Serious treatment-emergent AEs by SOC and PT

In addition to the by-treatment AE summaries, data listings will be provided for the following:

- Pre-treatment AEs
- Treatment-emergent AEs
- Post-treatment AEs
- OLE treatment-emergent AEs
- SAEs
- Liver events
- AEs leading to discontinuation or interruption of study drug
- Deaths
- Grades 2-4 albumin events

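### Month-only AE start dates in the month of the first OLE dose default to day 01, so events that began after that dose are counted in the double-blind safety table

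*SAP*

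**What the plan says.** SAP 10.1.5.2 handles incomplete AE start dates as follows:

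- **Day missing.** The start becomes the first dose date, "provided the start month and year are the same as the first dose of study drug" and the stop date is later than that dose or absent. If not, "Otherwise, the missing day portion will be estimated as" 01.
- **Day and month missing.** The first dose date is used, "provided the start year is the same as the first dose of study drug", under the same stop-date condition. Otherwise 1 January is used.
- **Nothing recorded.** If the stop date is after the first dose or is also absent, "the start date will be estimated to be the first day of study drug dosing".

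SAP 10.1.5.1 and 10.1.6 then assign the period. A treatment-emergent AE starts between the first dose and a limit given as "on or before the date of 6 weeks (42 days) post the last dose of study drug". OLE treatment-emergent AEs are "AEs that either started on or after the date of the first dose of study drug in the OLE". For the tables, "Double-blind treatment period AE summaries will present treatment-emergent AEs which occurred before study drug administration during OLE study period", or before the primary lock if that is earlier.

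SAP 5.2, 10.1.5.1 and 10.4 all specify the OLE explicitly when they mean the first OLE dose. SAP 10.1.5.2 does not, so its anchor is Day 1 of the double-blind period. Neither document gives a separate rule for partial AE dates in the OLE.

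**The concern.** For the first dose, the SAP resolves an ambiguous start date towards being on treatment. It does not do the same for the first OLE dose. An ambiguous date there goes to the 1st of the month, which is nearly always before the dose, so the event is booked to the double-blind period whatever its stop date.

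This matters most for participants randomised to placebo who enter the OLE. The first OLE dose is their first exposure to RVT-1401, yet an event that begins after it can appear in the placebo column of the controlled safety table and be missing from the OLE treatment-emergent table. Safety and tolerability over the 6-week treatment period is a primary objective, and the placebo column has about 7 people.

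The wording of SAP 10.1.5.1 suggests an oversight. The general treatment-emergent definition has a branch for events without a recorded start date. The OLE definition opens with an either but has no second branch.

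**Working it through.** The documents give no figure on this point, so there is nothing to reproduce. The check applies the rules as written.

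**Inputs**
- First OLE dose at Week 8 (Protocol 5.1). Week 2 is Day 8 and Week 6 is Day 36, so Week 8 is Day 50, or 49 days after Day 1. With the ±2-day visit window the gap is 47 to 51 days.
- Last double-blind dose on Day 36, so the 42-day limit counted from it is Day 36 + 42 = Day 78.
- Arm for the safety tables: treatment received in the double-blind period (SAP 5.1, 5.3).
- Planned sizes: 7 placebo and 14 active (Protocol 10.1; SAP 1.3), randomised 1:1:1, so 7 per arm.
- Illustrative calendar: every first-dose date in 2019 and 2020, 731 dates.

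**Step 1: which branch applies.** The shortest gap, 47 days, exceeds the longest month, 31 days. The first OLE dose shared a calendar month with the first dose on 0 of 731 dates. The day-01 fallback therefore always governs the OLE start month when the month is known.

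**Step 2: is day 01 before the OLE dose?** Yes, unless the dose was given on the 1st. Two years contain 24 such days, and 24/731 = 3.3%, so the imputed date precedes the OLE dose on 96.7% of dates.

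**Step 3: is the event still treatment-emergent?** Day 01 lies 0 to 30 days before the OLE dose. From Day 50 that is Day 20 to Day 50; with the visit window it is Day 18 to Day 52. All of these are after Day 1 and before Day 78. The event therefore enters the double-blind table whenever its imputed date precedes the OLE dose and the primary lock does not come first.

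**Example.** First dose 15-Jan-2020, first OLE dose 04-Mar-2020, AE start recorded as ??-Mar-2020. The imputed start is 01-Mar-2020 (Day 47), which is double-blind treatment-emergent even if the event stopped weeks later.

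**Step 4: share of unknown-day events affected.** Assume onsets spread evenly from the first OLE dose to Week 12. About 51% of true OLE-period onsets with an unknown day then move to the double-blind period. Those in later calendar months stay in the OLE. In the OLE start month itself, about 48% of days fall before the OLE dose on average, and day 01 puts onsets on those days in the correct period.

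**Step 5: size in a table row.** One added participant is 1/7 = 14.3 percentage points in the placebo column or in a single active arm, and 1/14 = 7.1 points in the combined active column.

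**Step 6: effect of an OLE anchor.** If the start is set to the first OLE dose when month and year match, the 51% falls to 0%. The cost is that some true pre-OLE onsets in that month move the other way.

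**The case against.** A reader might infer that every month-only AE in the OLE start month is misplaced. The rules do not support that. Some of these events did begin before the OLE dose, and for them day 01 gives the right period. The same holds for any event whose stop date is before that dose.

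A reader might also infer that the rule narrows the drug-placebo difference. That is not shown. The fallback applies to all three arms, and former 340 mg and 680 mg participants have events moved into their own double-blind columns as well. Inflation of the placebo column is possible, but its net effect against the active columns depends on event rates that the documents do not give.

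Four further points stand:
- AEs are collected at every visit (Protocol 8.2), source records must hold AE start and end dates (Protocol 13.1.5), and data cleaning is planned (Protocol 9). Partial dates should be few.
- Injection site reactions are assessed about 10 minutes after dosing and summarised separately by visit (SAP 10.1.7).
- Each participant counts once per summary, so someone already in a row adds nothing to it.
- Whole-study tables are unaffected, and the AE summaries carry no test or decision rule.

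The strongest objection is to a simple fix. Under SAP 10.1.5.2 an unknown stop day becomes the last day of the month and a missing stop date becomes the last known date on study. A test on the imputed stop date would screen out almost nothing, and true pre-OLE events, including active-arm ones, would leave the controlled table. The fix must allow for this.

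None of these points supplies the missing OLE rule.

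**Conclusion.** The gap is real and minor. As written, SAP 10.1.5.2 assigns the wrong period to a month-only AE that truly began on or after the first OLE dose in that dose's calendar month, unless dosing was on the 1st. The event is added to the double-blind column of the participant's original arm and lost from the OLE table. For placebo switchers an on-drug event is charged to placebo.

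The effect on one placebo row is at most 14.3 percentage points per affected participant, assuming 7 placebo participants and someone not already counted in that row. The number of such events is unknown and probably small. No claim about the overall direction of bias is justified.

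The conclusion rests on reading the first dose of study drug as Day 1, which the wording elsewhere in the SAP supports. The 51% figure depends on evenly spread onsets and is illustrative. Starts known only to the year, or not at all, also lack an OLE anchor: they go to Day 1, to 1 January or, where the stop date rules out Day 1, to the start of the stop year.

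**What to change.** Add a rule to SAP 10.1.5.2 for OLE participants. Impute the start to the first OLE dose date, and class the AE as OLE treatment-emergent, when all of these hold:

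1. The partial start date has the same month and year as the first OLE dose.
2. The stop date as recorded, not as imputed, is missing or is not before that dose.
3. The AE was not already reported at a visit before that dose.

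Flag these events in the listings so that a reader can recount them under either period.

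State how a recorded stop date with an unknown day in that month is treated. If it is treated as missing, the third condition does the screening. That condition needs the visit of first report to be recoverable from the database, which should be confirmed. The same drafting pass could settle year-only and absent start dates and the matching single-anchor rule for concomitant medications in SAP 10.4.

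The cost is a short SAP edit and a small programming change, best made before the primary lock. The downside is that some true pre-OLE onsets, including active-arm events, will move to the OLE table. The second and third conditions limit this, and the convention then matches the one already used for Day 1.

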10.1.6. Summaries of Adverse Events

All AE summaries will be provided separately for the double-blind treatment period and the follow-up period as well as the OLE treatment period and OLE follow-up period. Double-blind treatment period AE summaries will present treatment-emergent AEs which occurred before study drug administration during OLE study period or before the primary lock date, whichever comes first. Follow-up period AE summaries will present post-treatment AEs, OLE treatment period AE summaries will present OLE treatment-emergent AEs which occur before or on week 12 visit and OLE follow-up period AE summaries will present OLE post-treatment AEs. Pre-treatment AEs will be listed.

Overall summaries of treatment-emergent AEs by treatment group will be provided to include the number and percentage of subjects who:

1. Had any AE,
2. Had any Grade 3 or higher AE,
3. Had any treatment-related AE,
4. Had any Grade 3 or higher treatment-related AE,
5. Had any SAE,
6. Had any treatment-related SAE,
7. Permanently discontinued from study drug due to an AE, and
8. Died.

Summaries (number and percent of subjects) of treatment-emergent adverse events (by SOC, and PT) will be provided by treatment group for the following:

- All AEs,
- All Grade 3 or higher AEs,
- All treatment-related AEs,
- All Grade 3 or higher treatment-related AEs,
- All SAEs,
- All treatment-related SAEs,
- All AEs that leading to permanently discontinued from study drug.

Multiple events will be counted once only per subject in each summary. For data presentation, SOC will be ordered alphabetically, with PT sorted by decreasing frequency in

the combined RVT-1401 column. Treatment period and follow-up period AE summaries will be provided for the SAF analysis population. Open-label extension AE summaries will be provided for the OLE analysis population. Whole study AE summaries include the double blinded period, OLE period and follow up will be provided for below 3 tables:

- Overall summaries of treatment-Emergent AEs
- Treatment-emergent AEs by SOC and PT
- Serious treatment-emergent AEs by SOC and PT

In addition to the by-treatment AE summaries, data listings will be provided for the following:

- Pre-treatment AEs
- Treatment-emergent AEs
- Post-treatment AEs
- OLE treatment-emergent AEs
- SAEs
- Liver events
- AEs leading to discontinuation or interruption of study drug
- Deaths
- Grades 2-4 albumin events

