3. TYPE OF PLANNED ANALYSIS AND ALPHA ALLOCATION

Per protocol, an interim analysis will occur after the last subject completes the Week 7 visit of the study. All efficacy endpoints will be evaluated for this analysis. It is noted that the planned interim/primary analysis is the final analysis of the complete dataset from the double-blind treatment period. The database is interim due to the follow-up period, in which safety data will continue to accrue and be updated.

Due to COVID-19 impact on the study, an interim analysis may be done after 15 subjects have completed Week 7, although the study is continuing. An interim analysis plan (IAP) will guide any interim analysis that is done. The IAP will document disclosure and safeguards to protect the integrity of the ongoing study.

A final analysis will occur when the last subject completes or discontinues the study and the database is locked.

An additional analysis of the anti-RVT-1401 antibody data will be performed if any subjects require follow-up testing. This analysis will focus solely on the antibody data and does not require any alpha correction. The CSR will be amended with this additional analysis if it is necessary.

Alpha is controlled through the conditional sequencing of hypotheses. No other adjustment for multiplicity is needed. The interim analysis, if done, will be executed for administrative purposes due to business needs in response to circumstances precipitated by COVID-19 issues. Alpha is allocated for the interim analysis of 0.0001, which is considered to be negligible; consequently, the final analysis has alpha = 0.05 preserved.

4. **BLINDING**

At the time of the finalization of this SAP, no unblinding of any kind has occurred. It is noted that the only unblinded personnel for the study are documented in planning documents. Immunovant supports strong process and has standard operating procedures (SOPs) consistent with written regulatory guidance and standard conventions to protect the blinding of this study.

Selected laboratory analytes that may reveal the treatment for individual subjects are conveyed and stored in protected spaces with controlled access to safeguard further the treatment given to specific subjects.

There are four sources of unblinding or potential unblinding for this study:

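### Read literally, the primary-lock cut can leave a treatment-emergent AE in no period table; separately, the double-blind AE table spans nominal Days 1–49 or 1–78 depending on OLE entry

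*SAP*

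**What the plan says.** Three rules in the SAP decide which period table an AE enters.

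- **Double-blind tables** (SAP 10.1.6) present "treatment-emergent AEs which occurred before study drug administration during OLE study period or before the primary lock date, whichever comes first".
- **Treatment-emergent status** (SAP 10.1.5.1) runs from the first dose and ends "on or before the date of 6 weeks (42 days) post the last dose of study drug". The next category is "Post-treatment: AEs that started after the date of 6 weeks (42 days) post the last dose of study drug".
- **Follow-up tables** (SAP 10.1.6): "Follow-up period AE summaries will present post-treatment AEs".

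The OLE tables are to show "OLE treatment-emergent AEs which occur before or on week 12 visit and OLE follow-up period AE summaries will present OLE post-treatment AEs". SAP 10.1.5.1 defines four categories. OLE post-treatment is not among them, and OLE treatment-emergent has no end date.

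On timing, SAP 3 says that "an interim analysis will occur after the last subject completes the Week 7 visit of the study". It calls that database interim because of the follow-up period, "in which safety data will continue to accrue and be updated", and it plans a final analysis after the last participant finishes. Neither SAP 3 nor SAP 10.1.6 says whether the lock cut still applies to the double-blind tables in that final analysis.

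As a backstop, SAP 10.1.6 adds: "Whole study AE summaries include the double blinded period, OLE period and follow up will be provided for below 3 tables". These are the overall summary, all treatment-emergent AEs by system organ class and preferred term (SOC/PT), and serious ones by SOC/PT. Listings are also planned.

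**The concern.** The period tables should between them account for every treatment-emergent AE, and the double-blind table should observe the arms on a comparable footing. Two features of the rules work against this.

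First, the lock date ends the double-blind table, but the follow-up table does not start there. It starts 42 days after the last dose. A participant outside the OLE whose 42 days are still running at the lock has a stretch that belongs to neither table.

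Second, OLE entrants leave the double-blind table at their first OLE dose, while the others stay in it until the 42-day limit. Taking up the OLE is decided after randomisation (Protocol 5.1), so a crude percentage in this table partly reflects how long people were observed.

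Safety is a primary objective, and Protocol 10.3.3 promises AE summaries by study part and treatment group. The double-blind tables are where the randomised arms are compared before open-label drug.

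**Working it through.** **Inputs.** Week 6 is Day 36 (Protocol 8.1) and holds the last double-blind dose (SAP 1.2). The first OLE dose is at Week 8 (Protocol 5.1), with further doses at Weeks 10 and 12. The treatment-emergent limit is last dose + 42 days (SAP 10.1.5.1). The primary analysis follows the last participant's Week 7 visit (SAP 3). The lock date is not given.

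**Calendar.** Day of Week w = 7(w − 1) + 1. This reproduces the tabulated Days 8, 15, 22, 29 and 36 for Weeks 2 to 6, and gives Week 7 = Day 43, Week 8 = Day 50, Week 12 = Day 78 and Week 18 = Day 120. The SAP's own figure also checks: 6 weeks × 7 = 42 days.

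**Windows without lock truncation, last dose on Day 36.**
- Not in the OLE: 36 + 42 = Day 78, so Days 1–78, or 78 days.
- OLE entrant: before Day 50, so Days 1–49, or 49 days.
- Difference 78 − 49 = 29 days; ratio 78/49 = 1.59. Visit windows move each end by a day or two.

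**Effect of the lock.** Let L be the days from the last participant's Week 7 visit to the lock, and d the days by which a given participant was first dosed earlier than that last participant. The lock falls on the participant's own Day 43 + L + d, and onset must precede it, so the last covered day is 42 + L + d.
- Gap, not in the OLE: 78 − (42 + L + d) = 36 − L − d, floored at 0.
- Gap, OLE entrant first dosed in the OLE after the lock: 49 − (42 + L + d) = 7 − L − d, floored at 0.

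| L + d | Double-blind window, not in OLE | Double-blind window, OLE entrant | Gap days, not in OLE | Gap days, OLE entrant |
|---|---|---|---|---|
| 0 | 42 | 42 | 36 | 7 |
| 7 | 49 | 49 | 29 | 0 |
| 14 | 56 | 49 | 22 | 0 |
| 28 | 70 | 49 | 8 | 0 |
| 35 | 77 | 49 | 1 | 0 |
| 36 or more | 78 | 49 | 0 | 0 |

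For L + d from 7 to 36, the excess window (L + d − 7) and the gap (36 − L − d) always add to 29. A later lock closes the gap only by widening the difference in windows.

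**One event traced.** Take a participant not in the OLE with L + d = 14, so the lock is on Day 57, and an AE starting on Day 60. It is treatment-emergent (60 ≤ 78). It is not in the double-blind table (60 is not before 57), not in the follow-up table (60 is not after 78), and not in an OLE table. If it is Grade 3, it is counted in the whole-study overall summary and the whole-study SOC/PT table of all treatment-emergent AEs. It is in no Grade 3 or higher SOC/PT table, because that table exists only by period. The same holds for the treatment-related and discontinuation SOC/PT tables.

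**When windows affect the arm comparison.** With OLE uptake p in an arm, the average window is 49p + 78(1 − p) = 78 − 29p days. Two arms therefore differ by 29 × (difference in uptake). That is 0 with equal uptake, 29/7 = 4.1 days if uptake differs by one participant in an arm of 7, and at most 29. Uptake is not stated, so this is an illustration only.

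**OLE post-treatment.** Read as onset after the Week 12 visit, it leaves no gap. Under the 42-day rule, the limit for a participant with three OLE doses is 78 + 42 = Day 120, the Week 18 visit, so the OLE follow-up table would be nearly empty.

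**The case against.** The natural reading of SAP 3 is that the lock cut defines the primary output only, since safety data are updated afterwards and a final analysis follows. Even read literally, the cut reaches only late enrollees (L + d below 36). The primary safety objective concerns a 6-week treatment period, and the shortest window in the table above is Days 1–42, so that period is nominally covered for everyone.

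Unequal windows need differential OLE uptake to bias the arms. The documents give no reason to expect it: the OLE is open to completers of every arm, and the revealing laboratory values stay blinded to sites during it (Protocol 7.3). The group outside the OLE may be small, as SAP 5.1 makes a 12-week follow-up analysis depend on its size. Injection site reactions, the most frequent AE in the earlier studies (Protocol 3.2.3.1), have their own summary, and participants outside the OLE get no injections after Week 6. SAP 10.1.6 specifies counts and percentages, with no test.

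All of this stands and limits the weight of the point. It does not remove it. SAP 10.1.6 states the cut without restriction, so a programmer who follows it drops events from the period tables. Restricting the cut would still leave 49 against 78 days.

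The Day 36 condition also matters. Only completers may enter the OLE (Protocol 6.4), so the group outside it includes early stoppers. For a last dose on Day 1 the limit is Day 43, which is shorter than 49 days.

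A reader might also infer a hole in the OLE tables on Days 79–120. That follows only under the 42-day reading. The Week 12 reading matches the 6-week OLE follow-up in SAP 6.1, so all that is missing is a definition.

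**Conclusion.** Minor, and it holds in two parts.

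1. As written, a treatment-emergent AE can fall in no period table. For a participant outside the OLE with a Day 36 last dose, the gap is between 36 and 0 nominal days, depending on a lock date the documents do not give. For an OLE entrant it is at most 7.
2. Without lock truncation, and again for a Day 36 last dose, the double-blind table observes participants for 49 or 78 nominal days. The arm comparison is distorted if OLE uptake differs by arm. With no uptake or AE rates stated, the size cannot be computed. For scale, one participant in an arm of 7 is 1/7 = 14 percentage points.

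Two stronger readings are tempting and not supported. One is that AEs disappear from the study. They do not: the listings and the three whole-study tables keep them, and only the period tables, including SOC/PT tables with no whole-study version, lose them. The other is that the lock date confounds the arms through enrolment date. Enrolment date is fixed before randomisation, so on average it is balanced between arms.

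**What to change.** - In SAP 10.1.6, state that the primary-lock cut applies only to the primary-analysis output and is dropped in the final analysis. This takes one sentence and closes the gap.
- Keep the 42-day treatment-emergent table. Alongside it, either add a double-blind comparison over a common window (first dose to before the first OLE dose, or to before nominal Day 50 if not in the OLE), or show observation time or exposure-adjusted rates by arm. Replacing the 42-day window altogether would be partly a matter of preference. Events on Days 50–78 outside the OLE are still free of open-label drug, and IgG is expected to take 6 to 8 weeks to return to baseline (Protocol 3.2.2).
- As a clarification, define OLE post-treatment in SAP 10.1.5.1, for example as onset after the Week 12 visit.

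The cost is SAP wording, programming flags and, for the common window, one extra set of tables. No new data are needed.
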